3.6 OTHER ANALYSES

3.6.1 Other variables and/or parameters

3.6.1.1 PK analyses

The PK analyses will be performed on the PK population.

Serum concentrations of dupilumab will be summarized using arithmetic and geometric means, SD, standard error of the mean (SEM), coefficient of variation (CV), minimum, median and maximum per visits by each dose regimen group and overall. If date and/or time of the drug intake and/or sampling are missing, then the concentration will not be taken into account. When concentration values are below the lower limit of quantification (LLOQ), one-half of the LLOQ will be used except that the pre-dose concentration value at Week 0 will be used as 0 if the pre-dose concentration values at Week 0 are below the lower limit of quantitation. Values will be expressed in the tables with no more than three significant figures.

3.6.1.2 Immunogenicity analyses

The ADA analyses will be performed on the ADA population.

Samples for ADAs are collected at Week 0, Week 12, Week 24, Week 52/EOT, Week 64/EOS and/or early termination.

ADA incidence will be classified as the following:

- Pre-existing immunoreactivity is defined as: an ADA positive response in the assay at baseline with all post treatment ADA results negative, OR an ADA positive response at baseline with all post treatment ADA responses less than 4-fold over baseline titer levels.
- Treatment-emergent response is defined as: a positive response in the ADA assay post first dose, when baseline results are negative or missing. Treatment-emergent ADA responses are further classified as Persistent, Indeterminate or Transient.
 - Persistent Response - defined as a treatment-emergent ADA response with two or more consecutive ADA positive sampling time points, separated by greater than ($>$) 12-week period (84 days), with no ADA negative samples in between.
 - Indeterminate Response - defined as a treatment-emergent response with only the last collected sample positive in the ADA assay
 - Transient Response - defined as a treatment-emergent response that is not considered persistent OR indeterminate
- Treatment-boosted response is defined as: a positive response in the ADA assay post first dose that is greater-than or equal to 4-fold over baseline titer levels, when baseline results are positive.

Titer value categories are as following:

- Low (Titer $<1,000$)
- Moderate ($1,000 \leq \text{Titer} \leq 10,000$)
- High (Titer $>10,000$)

Samples that are positive in the ADA assay will be further characterized for the presence of anti-dupilumab neutralizing antibodies (NAb).

ADA negative is defined as ADA assay is negative at all times or exhibit a pre-existing immunoreactivity.

ADA positive is defined as either treatment-boosted or treatment-emergent response in the ADA assay.

The following summary will be provided based on ADA population during treatment-emergent period by each dose regimen group and overall:

- Number (%) of participants negative in the ADA assay at baseline of the study.

- Number (%) of participants positive in the ADA assay at baseline of the study:
 - The summary statistics (including number, median, Q1, Q3, minimum and maximum) of the titer for the participants positive in the ADA assay at baseline,
 - Number (%) of participants with neutralizing antibody status (negative or positive in the NAb assay).
- Number (%) of participants with ADA status (negative or positive in the ADA assay) at time points analyzed:
 - The summary statistics (including number, median, Q1, Q3, minimum and maximum) of the peak post-baseline titer for ADA positive participants,
 - ADA titers using descriptive statistics (including number, median, Q1, Q3, minimum and maximum) at ADA time points analyzed,
 - Number (%) of participants with neutralizing antibody status (negative or positive in the NAb assay) for the ADA positive participants.
- Number (%) of participants with pre-existing immunoreactivity.
- Number (%) of participants with treatment-boosted anti-drug antibodies:
 - The summary statistics (including number, median, Q1, Q3, minimum and maximum) of the peak post-baseline titer for treatment-boosted ADA participants.
- Number (%) of participants with treatment-emergent ADA:
 - The summary statistics (including number, median, Q1, Q3, minimum and maximum) of the peak post-baseline titer for treatment-emergent positive participants,
 - Number (%) of participants in the low, moderate or high titer category with treatment-emergent positive response,
 - Number (%) of participants with transient, indeterminate, or persistent treatment-emergent ADA response.
- Number (%) of participants with neutralizing antibody results (negative or positive in the NAb assay).

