17.7.2.5.2 Duration of study participation

17.7.2.5.2.1 Duration of study participation for each patient

The total duration, per patient, is of approximately 68 weeks.

For each patient, this includes the following 3 periods:

- **Screening period:** 4 ±1 weeks.
- **Treatment period:** 52 weeks open-label treatment (1 year) with last dosing at Week 50 for q2w and at Week 48 for q4w.
- **Post-treatment period:** 12 weeks.

17.7.2.5.2.2 Determination of end of clinical trial (all patients)

See [Section 6.2.2](#).

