17.7.2.9 Study procedures

The substudy consists of 3 periods:

- Screening period (Visit 0).
- Open-label treatment period (52 weeks; Visits 1-10).
During the open-label treatment period, patients will continue their background therapy dose regimen used during screening period.
- Post-treatment period (12 weeks; Visit 11).

The study visits occur on the planned dates (relative to the first injection), as scheduled. The visit schedule should be adhered to within ± 3 days in the treatment period and ± 1 week for the remaining study period.

Spirometry should be done at the study site approximately the same time of the day (preferably in the morning, but it could be done at a different time of the day). Spirometry should be performed at visits as detailed in [Section 17.7.2.8.2.1](#).

Once every 2 weeks IMP administration must be separated by at least 11 days. Once every 4 weeks IMP administration must be separated by at least 25 days. The treatment period visits occur q2w up to Visit 3 (Week 4), q4w up to Visit 8 (Week 24), and approximately every 12-16 weeks up to the EOS visit as detailed in [Section 17.7.2.7.1.3](#).

See [Section 17.7.2.7.1.3](#) for Investigational medicinal product administration.

At the time of permanent treatment discontinuation, patients will perform the ETD visits including early EOT visit and early EOS visit. Early EOT will be performed 2 weeks (with a ± 3 days window) after last IMP injection whenever possible. If the time of decision taken for permanent IMP discontinuation is >2 weeks after last IMP injection, this early EOT visit should be scheduled as early as possible from permanent discontinuation of IMP decision.

All the assessments defined for the EOT Visit 10 will be performed during this early EOT. Early EOS visit will be performed 12 weeks after early EOT visit with a ± 1 week window. All the assessment defined for the EOS Visit 11 will be performed during this early EOS visit.

Patients should be reminded that sexually active patients of reproductive potential are required to practice effective contraception during the entire study duration, while taking dupilumab and for 12 weeks post last IMP dose.

Patients who discontinue early from treatment may be asked to return to the clinic to have additional ADA samples collected for analysis based on the overall assessment of antibody titers and clinical presentation at the time of discontinuation.

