2.4.5 Analyses of safety data

The summary of safety results will be presented for each analysis set ([Section 2](#)) of safety population by the treatment category, unless otherwise specified.

General common rules

All safety analyses will be performed on the safety population as defined in [Section 2.3.1](#), unless otherwise specified, using the following common rules:

- Safety data in patients who do not belong to the safety population (eg, exposed but not enrolled) will be listed separately (if applicable).
- The baseline value for safety parameters is defined as the original baseline from the parent study.

- In addition to the baseline values, the pre-dose measurements at Week 0 in LTS14424 will be presented in the by-visit summary/figure for laboratory, vital signs or ECG parameters. The pre-dose measurements at Week 0 are the last available measurements prior to the first IMP dose in LTS14424 study.
- The potentially clinically significant abnormality (PCSA) values are defined as abnormal values considered medically important by the sponsor according to predefined criteria/thresholds based on literature review and defined by the sponsor for clinical laboratory tests, vital signs, and ECG ([Appendix A](#)).
- PCSA criteria will determine which patients had at least 1 PCSA during the analysis set specific treatment-emergent adverse event period as defined in [Section 2](#), taking into account all evaluations performed during the treatment-emergent adverse event period, including non-scheduled or repeated evaluations. The number of all such patients will be the numerator for the on-treatment PCSA percentage.
- The treatment-emergent PCSA denominator for a given parameter will be based on the number of patients assessed for that given parameter in the treatment-emergent adverse event period for each analysis set of safety population by the treatment category.

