3 STATISTICAL ANALYSES

3.1 GENERAL CONSIDERATIONS

In general, continuous data will be summarized using the number, mean, standard deviation (SD), median, minimum, and maximum for observed data and the change from baseline. Categorical and ordinal data will be summarized using the count and percentage of participants.

The baseline values for efficacy, safety, PK, ADA and other endpoints are defined as the last available measurements prior to the first IMP dose if the participant is treated, or the last available value up to enrollment if the participant is not exposed to IMP.

Unless otherwise specified, all analyses will be performed on each dose regimen group and overall.

Observation period

The observation period will be divided into 4 segments:

- The **pre-treatment period** is defined as the period up to first IMP administration.
- The **treatment-emergent (TE) period** is defined as the period from the first IMP administration to the last IMP administration + 98 days for participants with IMP on 100 mg/200 mg q2w regimen, or to the last IMP administration + 112 days for participants on 300 mg q4w regimen. The treatment-emergent period includes the following 2 periods:
 - The **on-treatment period** is defined as the period from the first IMP administration to the last administration of the IMP + 14 days for participants with IMP on 100 mg/200 mg q2w regimen, or to the last administration of IMP + 28 days for participants on 300 mg q4w regimen.
 - The **residual treatment period** is defined as the period from the end of the on-treatment period to the end of the treatment-emergent period.
- The **post-treatment period** is defined as the period from the end of the treatment-emergent period.

The on-study observation period is defined as the time from start of intervention until the end of the study defined as the status date collected on e-CRF page “Completion of End of Study”.

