3.5.3 Additional safety assessments

3.5.3.1 Laboratory variables, vital signs and electrocardiograms (ECGs)

The following laboratory variables, vital signs and electrocardiogram (ECG) variables will be analyzed. They will be converted into standard international units.

- Hematology:
 - Red blood cells and platelets and coagulation: erythrocytes, hemoglobin, hematocrit, platelet count
 - White blood cells: leukocytes, with five-part differential count (neutrophils, lymphocytes, monocytes, basophils, eosinophils)
- Clinical chemistry:
 - Metabolism: glucose, total cholesterol, total protein, creatine phosphokinase (CPK), albumin
 - Electrolytes: sodium, potassium, chloride, bicarbonate
 - Renal function: creatinine, blood urea nitrogen
 - Liver function: alanine aminotransferase (ALT), aspartate aminotransferase (AST), alkaline phosphatase (ALP), total bilirubin
- Vital signs: systolic and diastolic blood pressure, heart rate, respiratory rate, body temperature, body weight, height.
- ECG variables: heart rate, PR, QRS, QRS axis, QT, QTc, RR.

Data below the lower limit of quantitation/detection limit (LLOQ) will be replaced by half of the LLOQ, data above the upper limit of quantification will be replaced by ULOQ value.

Quantitative analyses

When relevant, for laboratory variables, vital signs and ECG variables above, descriptive statistics for results and changes from baseline will be provided for each analysis window, the last value and the worst value (minimum and/or maximum value depending on the parameter) during the on-treatment period. These analyses will be performed using central measurements only for laboratory variables.

For each continuous parameter for laboratory variables and vital signs, mean change from baseline with corresponding standard error will be plotted over time.

Analyses according to PCSA

Potentially clinically significant abnormality (PCSA) analyses will be performed based on the PCSA list currently in effect at Sanofi at the time of the database lock. For parameters for which no PCSA criteria are defined, similar analyses will be done using the normal range, if applicable.

Analyses according to PCSA will be performed based on the worst value during the treatment-emergent period, using all measurements (either local or central, either scheduled, nonscheduled or repeated).

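### The Japan SAP confines the ADA summary to a period that ends on the Week 64 target day, so read literally it excludes end-of-study samples taken late but within the visit window

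*SAP*

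**What the plan says.** Japan SAP 3.6.1.2 opens its list of ADA summaries with "The following summary will be provided based on ADA population during treatment-emergent period by each dose regimen group and overall". Japan SAP 3.1 defines that period as running "from the first IMP administration to the last IMP administration + 98 days" for the two q2w regimens, "or to the last IMP administration + 112 days for participants on 300 mg q4w regimen".

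Protocol 17.7.2.5.2 plans 52 weeks of treatment "with last dosing at Week 50 for q2w and at Week 48 for q4w". Protocol 17.7.2.9 counts visits from the first injection and allows plus or minus "1 week for the remaining study period" once treatment is over. ADA samples are scheduled at Weeks 0, 12, 24, 52 and 64.

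Four other places set no such end date:

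- Japan SAP 3.6.1.2 itself defines treatment-emergent and treatment-boosted responses by any qualifying positive after the first dose.
- Japan SAP 5.4, Table 8, assigns every ADA sample after Day 406 to Visit 11 (Week 64), with no upper limit.
- Main SAP 2.1.6 defines the same responses by results after the first dose in the current study.
- Protocol 17.7.2.10.4.4 calls for the ADA approach of the non-Japan full analysis set. That approach is in Protocol 11.4.4.2, which has no treatment-emergent limit.

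**The concern.** For a child who completes treatment, Week 64 is the only scheduled ADA sample in the follow-up period. Whether it counts affects ADA status, the peak titer and the persistent, indeterminate or transient class. Under the literal rule, that depends on a few days of scheduling, although the visit itself is within protocol.

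The error runs one way. The ADA population is defined without reference to the treatment-emergent period, so the denominator stays the same. Removing samples cannot create a treatment-emergent or boosted positive, so incidence can only fall. A child first positive at Week 64 would be reported as ADA negative.

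The substudy enrolled 13 participants, so one sample can change a reported category. Two programmers following different sentences of the same section could also produce different tables.

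**Working it through.** **Reproducing the plan's own figure.** With the first dose on Day 1, day = 7 × week + 1. EOS: 7 × 64 + 1 = 449, the target day in Table 8. The ±1-week tolerance gives Days 442 to 456, which is 15 permitted days.

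**End of the treatment-emergent period, last dose on schedule.**

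- q2w: last dose at Week 50 = 7 × 50 + 1 = Day 351; 351 + 98 = Day 449.
- q4w: last dose at Week 48 = 7 × 48 + 1 = Day 337; 337 + 112 = Day 449.

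Both coincide with the EOS target day, so Days 450 to 456 (7 of 15) fall outside.

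**Other last-dose dates.**

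| Situation | Period ends | EOS days outside, of 15 |
|---|---|---|
| Last dose 3 days late | Day 452 | 4 |
| Last dose 1 day late | Day 450 | 6 |
| On schedule | Day 449 | 7 |
| Last dose 1 day early | Day 448 | 8, including the target day |
| Last dose 3 days early | Day 446 | 10 |
| Final q2w dose missed (last at Week 48, Day 337) | 337 + 98 = Day 435 | 15 |
| Final q4w dose missed (last at Week 44, Day 309) | 309 + 112 = Day 421 | 15 |

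**Early discontinuation.** The early EOT visit falls 14 ± 3 days after the last dose, and early EOS falls 84 ± 7 days after that. With EOT exactly at 14 days, EOS falls 91 to 105 days after the last dose. On q2w (limit 98), 7 of 15 days are outside; the range is 4 to 10 as EOT moves from 3 days early to 3 days late. On q4w (limit 112), none are outside, because the latest EOS is 14 + 3 + 84 + 7 = 108 days after the last dose.

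**Share of completers affected.** The documents give no distribution of visit dates, so this part is assumption.

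- EOS day uniform over ±7 and last dose uniform over ±3: the average number of days outside is (10 + 9 + 8 + 7 + 6 + 5 + 4)/7 = 7, and 7/15 = 46.7%.
- Both uniform over ±3: (1 − 1/7)/2 = 3/7 = 42.9%.

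On 13 participants, if all complete and give a Week 64 sample, this is 13 × 0.467 = 6.1 or 13 × 0.429 = 5.6, so about 6.

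**Effect on the response classes.** A persistent response needs consecutive positives more than 84 days apart. Week 52 (Day 365) to Week 64 (Day 449) is exactly 84 days. With EOT on target and the last dose on schedule, only an EOS sample from Day 450 onward could confirm persistence from that pair, and those are the samples the rule removes.

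| Week 52 | Week 64 (Day 450 or later) | Class with Week 64 | Class without it |
|---|---|---|---|
| First positive | Positive | Persistent | Indeterminate |
| First positive | Negative | Transient | Indeterminate |
| Negative, as all earlier | Positive | Indeterminate | ADA negative |

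The table takes a child who is ADA negative at baseline, with EOT on Day 365.

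**Check of the remedy.** Counting every result after the first dose through EOS leaves 0 of the 15 permitted days outside.

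**The case against.** The strongest reply is that the restriction may never be applied. The definitions in the same section carry no end date, and Table 8 keeps any sample after Day 406. The lead-in also governs baseline ADA status, which is measured before dosing and so lies outside the treatment-emergent period. It therefore cannot be a strict filter on every item beneath it. This stands: a reader might infer that Week 64 samples are certain to be lost, and the documents do not establish that. They establish two incompatible rules.

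A reader might also infer that any EOS sample one day late is excluded. That holds only if the last dose was on or before schedule, because the cut-off follows the actual last dose.

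Timing limits the effect on the main report. Under Japan SAP 3.7, the core lock comes when all participants finish Week 52, and later follow-up goes to a CSR addendum. Some Week 64 samples will be absent from the core summary whatever this sentence says. No different ADA rule is given for the addendum, so the question carries over to it.

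Finally, a reader might extend the criticism to potentially clinically significant abnormalities (PCSA), which both SAPs tie to the same period: Japan SAP 3.5.3.1 says these analyses "will be performed based on the worst value during the treatment-emergent period", and main SAP 2.4.5 has a matching rule. The documents do not support calling that an error. Using one period for PCSA and for adverse events is coherent. Splitting them could make a late laboratory value a treatment-emergent PCSA while the adverse event recorded for it counts as post-treatment. Late EOS values still appear in the by-visit summaries, and the peak post-baseline eosinophil tables have no treatment-emergent limit. Only PCSA incidence and the trigger for the PCSA listing are cut.

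**Conclusion.** The point holds for the Japan ADA summary, as an internal contradiction with a known direction of error. The coincidence of dates is exact and follows from the documents alone: 7 of 15 permitted EOS days are excluded with an on-schedule last dose, 4 to 10 with a last dose within three days of schedule, and all 15 if the final dose is missed.

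The figure of a little under half of completers rests on symmetric scatter of EOS visits around the target day. It counts visits, not changed results; nothing in the documents shows how many ADA classifications would differ. The Week 12 FEV1 primary endpoint, the TEAE analysis and the main-study ADA analysis are untouched, and the ADA outputs are descriptive. The change should be made because it is nearly free and the affected group is very small, but it does not threaten the substudy's main conclusion.

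**What to change.** In Japan SAP 3.6.1.2, replace the limit to the treatment-emergent period with all ADA results after the first dose up to and including the EOS visit, and state that baseline ADA status comes from the pre-dose sample. State also that the rule applies to the CSR addendum, where Week 64 data collected after the core lock are reported. This agrees with the section's own definitions, Table 8, main SAP 2.1.6 and Protocol 17.7.2.10.4.4.

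Leave the treatment-emergent period for adverse events and the PCSA rules in both SAPs as they are.

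The cost is one sentence and minor reprogramming, with no new data. ADA incidence may come out slightly less favourable.

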3.6.1.3 Biomarker analyses

Biomarkers will be analyzed on the safety population.

For blood eosinophil count, FeNO, and serum total IgE, descriptive statistics (including number, mean, median, standard deviation, Q1, Q3, minimum and maximum), change from baseline and percentage change from baseline over visits will be presented. In addition, the mean, mean change from baseline, median percentage change from baseline will be plotted across visits.

For antigen-specific IgEs with a positive (≥ 0.35 IU/mL) incidence of greater than 25% at baseline, values at each visit, absolute change from baseline and percent changes from baseline will be summarized in descriptive statistics. Values reported as below the LLOQ (lower limit of quantitation) will be imputed as a value one half of the LLOQ.

Number and percentage of participants with no positive (≥ 0.35 IU/mL) antigen-specific IgE result, with positive (≥ 0.35 IU/mL) result for only one antigen, and with positive (≥ 0.35 IU/mL) results for at least two antigens will be summarized by time point. Same analysis will also be performed using LLOQ as the threshold.

For blood eosinophil count, with subgrouping the participants into baseline EOS ≤ 0.5 Giga/L and >0.5 Giga/L, the mean change from baseline will be plotted over visits for each of the two subgroups and overall. And table showing number (%) of participants who have peak post-baseline EOS count ≥ 1 Giga/L, ≥ 3 Giga/L and ≥ 5 Giga/L will be presented for each of the two subgroups and overall.

